#### 4.7.2.5. Other Analyses

The number and percentage of patients belonging to each of the following criteria will be summarized by treatment group:

- Day 190 percent change in TMV from baseline  $\geq 10\%$
- Day 190 percent change in 6MWD from baseline  $\geq 10\%$
- Day 190 absolute change in 6MWD from baseline  $\geq 30$  m
- Day 190 percent change in time to complete 10mW/R from baseline  $\geq 10\%$
- Day 190 absolute change in time to complete 10mW/R from baseline  $\geq 0.5$  sec.
- Day 190 percent change in 4-stair ascend time from baseline  $\geq 10\%$
- Day 190 percent change in PUL composite (mean) time to perform 4 timed activities from baseline  $\geq 10\%$
- Day 190 absolute change in FSHD-HI total score from baseline  $\leq -8$
- Day 190 absolute change in FSHD-HI arm/shoulder sub-score from baseline  $\leq -8$  (BB patients only)
- Day 190 absolute change in FSHD-HI mobility sub-score from baseline  $\leq -8$  (TA patients only)
- Day 190 absolute change in FSHD-HI activity limitation sub-score from baseline  $\leq -8$

For each criterion listed above, Fisher's exact test will be used to compare the proportions of patients belonging to the individual criterion between the two treatment groups using a 0.1 significance level.

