#### 4.7.1.3. Motor Function

##### 4.7.1.3.1. Lower Leg Function Assessments

###### 10-Meter Walk/Run Test

- Time to complete 10-meter walk/run (seconds)

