###### 4-Stair Climb

- Ascending

- Time to ascending stairs (sec.)

- Number and percentage of patients belonging to the following grades:

1. Unable to climb 4 standard stairs
2. Climbs 4 standard stairs “marking time” (climbs one foot at a time, with both feet on a step before moving to next step), uses both arms on one or both handrails
3. Climbs 4 standard stairs “marking time” (climbs one foot at a time, with both feet on a step before moving to next step), using one arm on one handrail
4. Climbs 4 standard stairs “marking time” (climbs one foot at a time, with both feet on a step before moving to next step), not needing handrail
5. Climbs 4 standard stairs alternating feet, needs handrail for support
6. Climbs 4 standard stairs alternating feet, not needing handrail support
7. Not Done

- Descending

- Time to descending stairs (sec.)

- Number and percentage of patients belonging to the following grades:

1. Unable to descend 4 standard stairs
2. Descends 4 standard stairs “marking time” (climbs one foot at a time, with both feet on a step before moving to next step), uses both arms on one or both handrails
3. Descends 4 standard stairs “marking time” (climbs one foot at a time, with both feet on a step before moving to next step), using one arm on one handrail
4. Descends 4 standard stairs “marking time” (climbs one foot at a time, with both feet on a step before moving to next step), not needing handrail
5. Descends 4 standard stairs alternating feet, needs handrail for support
6. Descends 4 standard stairs alternating feet, not needing handrail support
7. Not Done

- **6-Minute Walk Test**
  - Cumulative distance traveled at 6 minutes (meters)
  - Cumulative distance traveled at 1 minute (meters)
  - Cumulative distance traveled at 2 minutes (meters)
  - Cumulative distance traveled at 3 minutes (meters)
  - Cumulative distance traveled at 4 minutes (meters)
  - Cumulative distance traveled at 5 minutes (meters)
- Gait Assessments

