#### 4.7.1.3.2. Upper Arm Functional Assessments

- Performance of upper limb (PUL) – Middle level elbow dimension score
  - Sum of the 9 items for this particular dimension (Maximum = 34). These include: “Hand(s) to Mouth”, “Hand(s) to table from lap”, “Move weight on table”, “Lifting light cans”, “Lifting heavy cans”, “Stacking light cans”, “Stacking heavy cans”, “Remove lid from container”, and “Tearing paper”.
  - Time to lift 5 light cans (sec.)
  - Time to stack 5 light cans (sec.)
  - Time to lift 5 heavy cans (sec.)
  - Time to stack 5 heavy cans (sec.)
  - Composite (or average) time to complete the following tasks: lift 5 light cans, lift 5 heavy cans, stack 5 light cans, and stack 5 heavy cans.
- a. Note that when deriving the average time to complete the selected tasks listed above, one or more of the times may be missing for a given patient at one or more time points. If such a scenario occurs, the average of the “non-missing” times should then be determined. For example, if the “Time to lift 5 light cans (sec.)” is missing for a patient at a particular time point (s), and the other 3 quantities are non-missing, then the average time to complete the selected tasks should be computed off of the 3 non-missing quantities.
- PUL high level/shoulder dimension (patients receiving ACE-083 in the BB muscle during the Part 2 open-label phase)
  - Shoulder domain score which represents the sum of the following 4 items that the patient is asked to do on the preferred side [either right or left side identified by patient to be done on the same side for all scheduled times]:
    - a. Largest weight patient can use to perform shoulder abduction to shoulder height (elbow to shoulder level)
    - b. Largest weight patient can use to perform shoulder abduction above shoulder height (elbow to eye level)
    - c. Largest weight patient can use to perform shoulder flexion to shoulder height (elbow to shoulder level)
    - d. Largest weight patient can use to perform shoulder flexion above shoulder height (elbow to eye level)

Each of the 4 components above is scored depending on the highest weight performed where scores are: 0 = Unable; 1 = Able no weights; 2 = 200 g; 3 = 500 g; 4 = 1000 g. The maximum score is 16.

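### Four of the eleven Day 190 threshold criteria in SAP 4.7.2.5 carry a sign that counts patients who became slower on the timed tests

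*SAP*

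**What the plan says.** SAP 4.7.2.5 (Other Analyses) asks for the number and percentage of patients in each arm meeting each of eleven Day 190 criteria, with Fisher's exact test at the 0.1 level for every one. Four concern elapsed times:

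- on the walk/run, in relative terms: "Day 190 percent change in time to complete 10mW/R from baseline $\geq 10" (percent)
- on the same test, in absolute terms: "Day 190 absolute change in time to complete 10mW/R from baseline $\geq 0.5$ sec"
- on the stairs, in relative terms: "Day 190 percent change in 4-stair ascend time from baseline $\geq 10" (percent)
- on the upper limb tasks, in relative terms: "Day 190 percent change in PUL composite (mean) time to perform 4 timed activities from baseline $\geq 10" (percent)

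SAP 4.7.1.3 defines the underlying variables as durations: "Time to complete 10-meter walk/run (seconds", "Time to ascending stairs (sec" and, for the PUL, "Composite (or average) time to complete the following tasks: lift 5 light cans" and the three other can tasks.

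The same list contains three criteria on measures where more is better, all with ≥ (TMV by 10%, 6MWD by 10%, 6MWD by 30 m), and four FSHD-HI criteria, of which the first reads "Day 190 absolute change in FSHD-HI total score from baseline $\leq -8".

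**The concern.** For a duration, a positive change from baseline means a slower patient. Read literally, the four timed criteria tabulate and test worsening, while the lines around them tabulate improvement. The Part 2 secondary objective (SAP 2.2) is whether ACE-083 improves motor function, so the comparison one would expect, the proportion who became faster, is not in the plan for these three measures.

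Two things are at stake. A programmer who follows the text will produce worsening rates in a table whose other rows are improvement rates. If the drug works, fewer ACE-083 than placebo patients will meet those rows, and a reader could take that as evidence against it. Also, if the sign is noticed only after unblinding, correcting it will look data-driven, although the SAP's stated purpose (Section 1) is to fix the analyses before database lock.

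**Working it through.** **1. Direction of each criterion.** Take change as Day 190 minus baseline, and percent change as 100 × (Day 190 − baseline)/baseline.

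| Criteria | Number | Threshold | Better direction | Criterion counts |
|---|---|---|---|---|
| TMV %, 6MWD %, 6MWD m | 3 | ≥ positive | higher | improvement |
| FSHD-HI total and three sub-scores | 4 | ≤ -8 | lower (Protocol 12.4 links the score to disease burden) | improvement |
| 10mW/R %, 10mW/R sec, 4-stair ascent %, PUL composite % | 4 | ≥ positive | lower | worsening |

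3 + 4 + 4 = 11. The four exceptions cover three measures.

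**2. Is there a convention that rescues them?** The FSHD-HI thresholds of -8 show that changes in this list are signed. SAP 4.1.5 explains how left and right changes are averaged but gives no formula that turns change into reduction. The 10-meter walk/run, 4-stair and PUL parts of SAP 4.7.2.2 analyse ordinary change from baseline in the same times. SAP Section 5 lists no special rule. Where the SAP wants a direction defined it does so, as for MRC-MMT grade in 4.7.2.2.

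**3. A single patient.** From 10.0 s to 8.5 s: change -1.5 s, or 100 × (-1.5)/10.0 = -15%. This patient is faster and fails both 10mW/R criteria. From 10.0 s to 11.5 s: +1.5 s, +15%. This patient is slower and meets both.

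**4. Illustration of size.** Section 4.7.2.5 states no computed figure. The nearest figure in the plan is the 83% power in SAP 4.1.1 (difference 10%, SD 9%, 12 per group, two-sided 0.10). A noncentral t with 22 degrees of freedom and noncentrality 10/(9 × √(2/12)) gives 83.9%, in agreement. Those inputs are for TMV and 6MWD; the documents give no mean or SD for any timed test, so the values below are assumptions. Changes are taken as normal with placebo mean 0.

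- As written: P(change ≥ 10) = 1 − Φ((10 − mean)/SD)
- Reversed: P(change ≤ -10) = Φ((-10 − mean)/SD)

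For mean -10%, SD 9%: as written, ACE-083 1 − Φ(20/9) = 1.3% and placebo 1 − Φ(10/9) = 13.3%; reversed, Φ(0) = 50.0% and 13.3%.

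The Fisher columns are exact enumerations, taking the test as two-sided. They give the probability of a significant result with fewer ACE-083 patients (as written) or more ACE-083 patients (reversed) meeting the criterion.

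| ACE-083 mean, SD | As written, ACE-083 v placebo | Reversed, ACE-083 v placebo | Fisher, written, n=14 / 12 per arm | Fisher, reversed, n=14 / 12 per arm |
|---|---|---|---|---|
| -10%, 9% | 1.3% v 13.3% | 50.0% v 13.3% | 8.8% / 5.5% | 52.0% / 51.0% |
| -5%, 9% | 4.8% v 13.3% | 28.9% v 13.3% | 5.5% / 3.7% | 14.7% / 12.9% |
| -10%, 15% | 9.1% v 25.2% | 50.0% v 25.2% | 17.3% / 13.9% | 22.5% / 25.9% |
| -5%, 15% | 15.9% v 25.2% | 36.9% v 25.2% | 7.4% / 6.6% | 7.6% / 8.9% |

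For the 0.5 sec criterion with an assumed SD of 1.0 sec: a mean of -0.5 sec gives 15.9% v 30.9% as written and 50.0% v 30.9% reversed; a mean of -1.0 sec gives 6.7% v 30.9% and 69.1% v 30.9%.

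**The case against.** The strongest reply is that SAP 4.7.2.5 never calls these criteria response or improvement; it only counts patients who meet them. The sponsor could have meant to count worsening, and the documents do not state the scoring direction of the FSHD-HI outright. This stands to a degree: intent is inferred. But a list that counts gains in walking distance beside losses in walking speed, without saying so, would be odd. If worsening was meant, the text still has to say so.

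Second, the harm is limited. The section is supplementary, the protocol's statistics section plans no threshold analysis, and the same measures are tested as signed continuous changes by ANCOVA with MMRM sensitivity in SAP 4.7.2.2. That is correct and caps the seriousness of the point. A misreading is possible, not certain, since the tables would show the criterion beside the counts.

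Third, the illustration rests on assumed values, and in three of its four percent scenarios the reversed test favours ACE-083 in only 7.6% to 22.5% of trials with 14 per arm. This also stands. The concern does not need those numbers: it follows from the sign alone.

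A text-conversion fault is unlikely. The minus sign in the FSHD-HI lines survived, and each timed line would need both its inequality and its sign misread.

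**Conclusion.** The concern holds. As written, four of the eleven criteria, on three timed measures, count patients who became slower and compare the arms on worsening. This is certain from the wording and the variable definitions. That improvement was intended is a strong inference from the other seven criteria and the Part 2 objective. Under the assumed percent scenarios, a drug that speeds patients up would show significantly fewer ACE-083 patients meeting a written criterion in 5.5% to 17.3% of trials with 14 per arm, and in 3.7% to 13.9% with the 12 completers per arm that the plan aims to secure. The written criterion would almost never favour the drug. The point should be fixed, but its reach is confined to these supplementary tables.

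**What to change.** Before database lock, change the four criteria in SAP 4.7.2.5 to:

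- 10mW/R time, percent change ≤ -10%
- 10mW/R time, absolute change ≤ -0.5 sec
- 4-stair ascent time, percent change ≤ -10%
- PUL composite time, percent change ≤ -10%

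Add the formula for absolute and percent change to SAP 4.1.5, and label the table rows as improvement.

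The alternative is to keep positive thresholds and define improvement as baseline minus Day 190 (percent: 100 × (baseline − Day 190)/baseline). In that case the four criteria themselves must be reworded as reductions in time; otherwise percent change from baseline would have opposite signs here and in 4.7.2.2. The first option is simpler.

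The cost is four edited lines or one definition, and the matching program lines. No further data are needed, and the sample size and ANCOVAs do not change.

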## **4.8. Pharmacodynamic Data**

### **4.8.1. Variables**

Pharmacodynamic data consists of the following selected laboratory data (e.g. CTX and hemoglobin).

### **4.8.2. Analyses**

#### **4.8.2.1. Part 1**

Individual pharmacodynamic data will be listed.

For each pharmacodynamic variable, raw data and changes from baseline will be summarized by dose cohort and scheduled time. Such summaries may be accompanied by a plot of mean  $\pm$  SEM. No imputations for missing data will be performed.

Additional analyses may be performed as appropriate.

#### **4.8.2.2. Part 2**

##### **Double-Blind Period**

Individual pharmacodynamic data will be listed.

For each pharmacodynamic variable, raw data and changes from baseline will be summarized by treatment group and scheduled time. Such summaries may be accompanied by a plot of mean  $\pm$  SEM. No imputations for missing data will be performed.

Additional analyses may be performed as appropriate.

##### **Open-Label Period**

Individual pharmacodynamic data will be listed.

For each pharmacodynamic variable, raw data and changes from baseline will be summarized by treatment sequence and scheduled time. Pooled summaries across treatment sequences will also be provided. Such summaries may be accompanied by a plot of mean  $\pm$  SEM.

No imputations for missing data will be performed.

Additional analyses may be performed as appropriate.

## **4.9. Safety Data**

### **4.9.1. Adverse Events**

Adverse events (AEs) will be coded using MedDRA Version 19.1.

All AEs will be listed and will include but not necessarily be limited to the following: verbatim term, MedDRA preferred term, treatment group, severity, relationship to study medication,

action taken with respect to study medication, and whether or not the AE is treatment-emergent although not necessarily in that order.

Treatment-emergent AEs (TEAEs) are defined those AEs that start or worsen in intensity on or after the first study drug administration up to the end of the follow-up period (Day 141 [Part 1] / Day 393 [Part 2]). AEs classified as TEAEs will be summarized. Planned summaries include the following (for each muscle group unless otherwise specified):

- Overall summary of TEAEs by treatment group
- Summary of TEAEs by MedDRA System Organ Class and Preferred Term for each treatment group – Number of Patients
- Summary of TEAEs by MedDRA System Organ Class and Preferred Term for each treatment group – Number of Events
- Summary of TEAEs by MedDRA Preferred Term for each treatment group – Number of Patients
- Summary of TEAEs by MedDRA Preferred Term for each treatment group – Number of Events
- Summary of CTCAE Grade 3 or Higher TEAEs by MedDRA System Organ Class and Preferred Term for each treatment group – Number of Patients
- Summary of CTCAE Grade 3 or Higher TEAEs by MedDRA System Organ Class and Preferred Term for each treatment group – Number of Events
- Summary of CTCAE Grade 3 or Higher TEAEs by MedDRA Preferred Term for each treatment group – Number of Patients
- Summary of CTCAE Grade 3 or Higher TEAEs by MedDRA Preferred Term for each treatment group – Number of Events
- Summary of TEAEs possibly or probably related to study drug by MedDRA System Organ Class and Preferred Term for each treatment group – Number of Patients
- Summary of TEAEs possibly or probably related to study drug by MedDRA System Organ Class and Preferred Term for each treatment group – Number of Events
- Summary of TEAEs possibly or probably related to study drug by MedDRA Preferred Term for each treatment group – Number of Patients
- Summary of TEAEs possibly or probably related to study drug by MedDRA Preferred Term for each treatment group – Number of Events
- Summary of TEAEs by MedDRA Preferred Term by CTCAE Grade and Relationship to Drug for each treatment group – Number of Patients
- Summary of TEAEs by MedDRA Preferred Term by CTCAE Grade and Relationship to Drug for each treatment group – Number of Events
- Summary of Serious Adverse Events – Number of Patients

#### 4.9.2. Clinical Laboratory Evaluations

The following table lists the planned clinical laboratory assessments:

Type of Assessment	Details
Hematology	Hemoglobin, hematocrit, platelet count, red blood cell count, white blood cell (WBC) count, and WBC differential
Chemistry	AST, ALT, lactate dehydrogenase (LDH) and isoenzymes 1-5, gamma-glutamyl transpeptidase (GGT), blood urea nitrogen (BUN), creatinine, creatine kinase (CK), myoglobin, aldolase, sodium, potassium, glucose, albumin, total bilirubin
Urine	Urinalysis by dipstick analysis (pH, specific gravity, protein, myoglobin, glucose, ketones, blood, leukocyte esterase, and nitrite)

In addition to the tests listed below, a urine pregnancy test is performed on all females of childbearing potential according to scheduled times listed in the protocol.

Descriptive statistics of raw data and change from baseline data will be provided by treatment group for each scheduled time.

Plots of individual patient data will be provided by treatment group and scheduled time for continuous laboratory data. Plots of mean  $\pm$  SEM will be provided for raw data and change from baseline data for the following selected laboratory data: hemoglobin, glucose, aldolase, blood urea nitrogen (BUN), creatinine kinase (CK), creatinine, and myoglobin.

Shift tables describing out-of-range shifts from baseline (in frequency counts) will be created for post-dose time points.

Additional analyses may be performed as appropriate.

#### Vital Signs

Vital sign parameters consist of weight, heart rate, systolic and diastolic blood pressure.

Descriptive statistics will be provided for raw data and absolute change from baseline by scheduled time for each treatment group. Post-dose recheck values will not be used for calculation of descriptive statistics.

With the exception of weight, plots of individual patient data will be provided by treatment group and scheduled time. Plots of mean  $\pm$  SEM will be provided for raw data and change from baseline data.

Additional analyses may be performed as appropriate.

#### Electrocardiogram

Twelve-lead electrocardiogram (ECG) parameters consist of the following: (heart rate, PR, QRS, QT, and QTc (Bazett correction)).

Descriptive statistics will be provided for raw data and absolute change from baseline by scheduled time for each treatment group. Post-dose recheck values will not be used for calculation of descriptive statistics.

Additional analyses may be performed as appropriate.

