Strength (QMT – by handheld device) ¹²	X	X	X	X	X	X	X	X	X	X	X	X	X	X	X	X	X		
Lower Leg Functional Assessments ¹³	TA & BB	TA & BB	TA		TA	TA	TA	TA	TA	TA	TA	TA	TA	TA & BB Day 190		TA	TA	TA & BB	
Upper Arm Functional Assessments ¹⁴	BB & TA	BB & TA	BB		BB	BB	BB	BB	BB	BB	BB	BB	BB	BB & TA Day 190		BB	BB	BB & TA	
FSHD-Health Index	X	X	X		X	X	X	X	X	X	X	X	X	X		X	X	X	
Monitoring of concomitant medications	X	X	X	X	X	X	X	X	X	X	X	X	X	X	X	X	X	X	
Monitoring of adverse events			X	X	X	X	X	X	X	X	X	X	X	X	X	X	X	X	
Randomization ¹⁵			X																
Study drug administration ¹⁶			X			X	X	X	X	X	X	X	X	X	X	X			
MMT assessment (MRC)	X													X			X	X	

¹ Study procedures must be done prior to administration of study drug. Reference the Study Manual for the order of study procedures. Laboratory samples and functional/strength assessments may be collected up to 24 hours prior to administration of study drug. Time of study drug administration is the time of the first injection. The Day 1 visit is timed relative to the Screening Day -28 to Day -21 visit. The Day -7 visit is timed relative to the scheduled Day 1 visit.

² All visit day windows should be considered relative to the date of the previous dose of study drug. Actual visit days may be different than planned (e.g., Day 8, Day 22) due to windows on visits and potential dosing delays.

³ Pregnancy test for women of childbearing potential to be performed and negative result confirmed before dosing.

⁴ Genetic testing for FSHD1/FSHD2 to be performed at screening if patient has not already had testing performed or previous results cannot be used to determine eligibility. Genetic testing for FSHD1/FSHD2 to be performed during the study if first degree relative is used for study eligibility but patient has not had testing previously performed or if patient's genetic documentation is inadequate with respect to FSHD1 D4Z4 fragment size or repeat number

⁵ Full physical examination includes skin, head, eyes, ears, nose, throat and neck, lymph nodes, cardiovascular, respiratory, gastrointestinal, musculoskeletal, and neurological

⁶ Limited physical examination includes skin, cardiovascular, respiratory, musculoskeletal and neurological assessments

⁷ Injection site examination including but not limited to evaluating erythema, pain, bruising, bleeding, and other signs of discomfort or skin reaction to be completed at least 30 minutes after injection.

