**Table 1: Planned Doses to Be Administered for Part 1**

Cohort	Dosing Days	Muscle	Planned Dose Level	Type of Administration	ACE-083 n
1a	1, 22, 43, 64, and 85	Tibialis Anterior	150 mg	Unilateral	6
2a	1, 22, 43, 64, and 85	Tibialis Anterior	200 mg	Unilateral	6
3a	1, 22, 43, 64, and 85	Tibialis Anterior	200 mg	Bilateral	6
Total Number of Patients (Planned)					18

Cohort	Dosing Days	Muscle	Planned Dose Level	Type of Administration	ACE-083 n
1b	1, 22, 43, 64, and 85	Biceps brachii	150 mg	Unilateral	6
2b	1, 22, 43, 64, and 85	Biceps brachii	200 mg	Unilateral	6
3b	1, 22, 43, 64, and 85	Biceps brachii	240 mg	Unilateral	6
Total Number of Patients (Planned)					18

Periodic reviews of selected blinded safety and imaging data will be reviewed by the Safety Review Team (SRT) in accordance with the SRT Guidelines.

### 3.2. Part 2

Prior to the initiation of Part 2, a review of the safety and efficacy data from Part 1 will be done in order to determine whether one or both the TA and BB muscles will be studied as well as the recommended dose level for each muscle. Up to 56 patients (28 patients per muscle) will be enrolled and randomized (1:1 ratio) to receive either ACE-083 (n=14/muscle) or placebo (n=14/muscle) bilaterally to either the TA or BB muscles (but not both). Patients will receive study drug once every three weeks for approximately 6 months (9 doses). If a patient discontinues the study for reasons other than a safety issue related to investigational study drug and the patient had not completed the Day 43 visit, the patient may be replaced. The replacement patient will receive the same treatment as the patient replaced.

Patients who complete the double-blind treatment period will immediately roll over to open-label treatment with ACE-083. All patients will receive ACE-083 administered at the same dose as in the double-blind period. They will receive bilateral injections, in the same muscles that study drug was administered to during the double-blind period, once every three weeks for approximately 6 months (8 doses). In Part 2, the SRT will periodically review blinded safety data for each muscle treated.

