**4.1.4. Definitions of Baseline****Part 1 and Part 2 (Double-blind phase)**

For MRI, PD, and safety data, baseline is defined as the last non-missing assessment prior to the first dose of study drug administration. Theoretically, this is the Day 1 pre-dose assessment. For patients that are randomized (applicable to patients participating in Part 2) but do not receive any study drug administration, the date of randomization will be the baseline reference.

For motor function data (lower leg and upper arm functional assessments), strength (QMT by handheld device), gait, and FSHD-HI data whose pre-treatment assessments are performed up to three times prior to the first dose, the baseline is defined as the average of the non-missing values. Theoretically, this would be at the Screening Day -28, Screening Day -7, and Day 1 visits. The first dose date will serve as the reference from which the non-missing pre-treatment values would be identified. For patients that are randomized (applicable to patients participating in Part 2) but do not receive any study drug administration, the date of randomization will be the baseline reference. The last non-missing assessment prior to the first dose of study drug administration will also be determined for this data and will be available for sensitivity analyses for any analyses of changes from baseline as appropriate.

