 MRI assessments should be completed within 5 days prior of the scheduled dose administration. MRI assessments during the follow up period (Day 358/ET and Day 393/EOS) have a ± 5 day window

 Maximum voluntary isometric contraction testing (MVICT) of both TA and BB muscles will be conducted for all cohorts at screening visits, Day 190 and Day 393/EOS. At all other visits, only the muscle under study will be tested (i.e., TA or BB). Both sides will be tested for all visits (right and left).

 TA cohort only: 10-meter walk/run, 4-stair climb, 6-minute walk test, and gait analysis are performed at all visits: 100-meter timed test begins at Day 169 and continues throughout open-label visits; lower leg assessments will be collected for the BB cohorts at screening visits, Day 190 and Day 393/EOS only.

 BB cohort only: PUL mid-level/elbow dimension performed at all visits; additional PUL high level/shoulder dimension begins at Day 169 and continues throughout open-label visits. PUL testing will also be performed on patients in TA cohorts at screening visits (mid level), Day 190 (high and mid-level) and Day 393/EOS (high and mid-level) only.

 Non-ambulatory patients in the BB cohort can opt out of the TA assessments.

 Randomization should occur within 24 hours prior to Day 1 dose.

 Study drug administration should occur within 21 days (± 3 days) of the last dose.

 Patients who discontinue prior to the Day 358/ET visit should complete the Day 358/ET visit at the time of discontinuation and return for the remaining follow-up period visit. If an MRI has been completed within 4 weeks of discontinuation, it does not need to be repeated as part of the Day 358/ET visit procedures.

 If a patient has a positive ADA result at Day 393/EOS, the patient will be asked to return to the clinical site for additional follow-up approximately every 3 months until a negative or stable result is obtained.

 ECG is to be conducted ±1 hour of the 4h PK sample.

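### Part 2 QTc is summarised with the Bazett correction only, so a heart-rate difference between pre-dose and post-dose ECGs can appear as a QTc change; Fridericia QTc should be added beside it

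*SAP*

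**What the plan says.** The Electrocardiogram part of SAP 4.9.2 gives the 12-lead parameters as "heart rate, PR, QRS, QT, and QTc (Bazett correction". The planned output is one sentence: "Descriptive statistics will be provided for raw data and absolute change from baseline by scheduled time for each treatment group". The only other provision is generic: "Additional analyses may be performed as appropriate". Neither the protocol nor the SAP names a second QT correction.

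For safety data, SAP 4.1.4 sets the reference value: "baseline is defined as the last non-missing assessment prior to the first dose of study drug administration". It adds that this should in theory be the Day 1 pre-dose value. In Protocol Table 6, however, the Part 2 ECG row as extracted shows Day -7, Day 2, Day 85 at 4 hours and Day 86, with nothing on Day 1. The last pre-dose ECG is then the Day -7 one. The Day 85 recording is tied to the pharmacokinetic draw: "ECG is to be conducted ±1 hour of the 4h PK sample".

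Part 1 schedules a single ECG, on Day 1, and the schedule's first footnote says "Study procedures must be done prior to administration of study drug". Part 2 has a concurrent control: patients are "randomized (1:1 ratio) to receive either ACE-083 (n=14/muscle) or placebo (n=14/muscle" (SAP 3.2).

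**The concern.** A QT correction is meant to remove the dependence of QT on heart rate. Bazett divides by the square root of RR. If QT actually varies with RR less steeply than that, Bazett QTc rises with heart rate even when repolarisation has not changed, and falls when heart rate falls. The planned summary is a change between ECGs taken at different visits, before and after dosing, and nothing in the planned QTc analysis checks whether such a change is a rate effect.

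What is at stake is how a descriptive safety table is read. A rate-driven change within an arm could be taken for QTc prolongation, or could mask a real one. If heart rate moved differently in the two arms, whether through the drug or by chance with 14 patients per arm and muscle, the difference would carry into the comparison with placebo.

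**Working it through.** The plan states no QTc figure, so there is nothing of its own to reproduce.

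**Inputs from the documents.** Bazett is the only correction; QT and heart rate are both recorded; Part 2 has a pre-dose ECG and three post-dose ECGs.

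**Assumptions, not in the documents.** True (rate-independent) QTc 380 to 420 ms; heart rate 60 to 85 bpm; QT proportional to RR^e with e from 0.30 to 0.50; no drug effect on repolarisation.

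**Formulas.** RR = 60/HR; QTcB = QT/RR^(1/2); QTcF = QT/RR^(1/3). Hence QTcB/QTcF = RR^(1/3 - 1/2) = RR^(-1/6) = (HR/60)^(1/6). With true QTc equal to q, QT = q × RR^e, so QTcB = q × RR^(e - 1/2) and QTcF = q × RR^(e - 1/3).

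**Step 1: q = 400 ms, e = 1/3.** At 60 bpm QTcB = 400. At 70 bpm QTcB = 400 × (70/60)^(1/6) = 410.4, a change of +10.4 ms.

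| Heart rate (bpm) | Change in QTcB (ms) | Change in QTcF (ms) |
|---|---|---|
| 60 to 65 | +5.4 | 0 |
| 60 to 70 | +10.4 | 0 |
| 60 to 75 | +15.2 | 0 |
| 70 to 80 | +9.2 | 0 |
| 70 to 85 | +13.5 | 0 |
| 70 to 60 | -10.4 | 0 |

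For a 10 bpm rise from 60 or 70 bpm, the range over q = 380 to 420 ms is +8.8 to +10.9 ms.

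**Step 2: relax the exponent (q = 400 ms, 60 to 70 bpm).** Step 1 assumes that Fridericia is exactly right, so it assigns all of the disagreement to Bazett.

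| e | Change in QTcB (ms) | Change in QTcF (ms) |
|---|---|---|
| 0.30 | +12.5 | +2.1 |
| 1/3 | +10.4 | 0 |
| 0.40 | +6.2 | -4.1 |
| 0.45 | +3.1 | -7.1 |
| 0.50 | 0 | -10.1 |

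To first order the two errors are proportional to (1/2 - e) and (1/3 - e). They are equal in size when 1/2 - e = e - 1/3, that is, at e = 5/12, about 0.42. Below that Fridericia is closer; above it Bazett is.

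**Step 3: which comparisons are exposed.** Within an arm, any change in heart rate from the pre-dose ECG enters the QTcB change. Between arms, only the difference in heart-rate change does. Part 1 has no scheduled post-dose ECG, so no scheduled change arises.

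**The case against.** The strongest reply is that nothing in the documents shows heart rate differing between the pre-dose and post-dose ECGs, and that is correct. A reader might infer an exertion effect, because Day 85 also carries strength and functional testing. The schedule does not support this. The Day -7 visit carries strength tests and both lower-leg and upper-arm tests. The first footnote to Table 6 lets functional and strength tests be done up to 24 hours before dosing. The Day 85 ECG comes about 4 hours after dosing, and the order of procedures is left to the Study Manual. The point needs some heart-rate difference, from whatever cause; it cannot claim that one is expected.

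The Day -7 reading can also be questioned. In the extracted tables some rows are displaced: the second MRI falls under Day 22, although the SAP's repeated-measures model places it at Day 43. In Protocol Table 6 the ECG row does line up with the pharmacokinetic row, including the Day 85 four-hour entry, but it should be checked against the typeset table. The arithmetic holds for any pre-dose ECG compared with a later one.

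Heart rate and uncorrected QT are summarised in the same output, and vital-sign heart rate separately, so a sizeable rate shift would be visible. This is a partial safeguard: it warns the reader but does not give a rate-adjusted QTc, and group means of QT and heart rate do not give the mean of a nonlinear correction exactly.

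Fridericia QTc could be derived later with no loss of data, and the SAP permits further analyses. That is so. But the SAP's stated purpose is to fix methods before database lock, and a second correction chosen after a Bazett signal has been seen is less persuasive.

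Finally, a reader might infer that Bazett should be replaced. Step 2 does not support that: for exponents above about 0.42 Fridericia has the larger error.

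**Conclusion.** The point holds as a minor one, for Part 2 only. With Bazett as the sole correction, a heart-rate difference between the pre-dose and post-dose ECGs can appear as a QTc change: about +9 to +10 ms for a 10 bpm rise from 60 or 70 bpm, with a similar false shortening for a fall. This rests on an assumed heart-rate shift, an assumed true QTc of 400 ms and QT varying as RR^(1/3). It shrinks to zero as the exponent approaches 0.5.

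A shift shared by both arms cancels against placebo. What remains is the within-arm change and any between-arm difference in heart rate, on whose size and direction the documents are silent. They do not support reading this as an expected false prolongation on ACE-083.

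No decision in the plan turns on QTc. The ECG summary is descriptive, there is no QTc threshold or test, and ECG does not appear in the safety-assessment list in Protocol 12.3 or in the safety analyses of Protocol 14.2.4.

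**What to change.** In the Electrocardiogram part of SAP 4.9.2, add QTcF = QT/(60/HR)^(1/3), derived for each ECG from the recorded QT and heart rate. Summarise raw values and change from baseline by scheduled time and treatment group, beside the Bazett values. Keep Bazett in the summaries: agreement between the two is reassuring, and disagreement flags a rate effect.

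The cost is one derived variable and its rows in the existing ECG tables. It needs no new ECGs or data and has no effect on sample size, significance level or power.
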